#### 8.4. Statistical methods

The change of quality of life measure from baseline will be examined by the t-test or the nonparametric rank-based test. The planned analyses will include descriptive statistics on the proportions of responses (*i.e.* % subjects with treatment response) and the time to response. The response probabilities will be estimated using the sample proportions and their inferences including confidence intervals and hypothesis testing will be evaluated using Binomial distributions.

The time to responses and the progression-free survival will be analyzed using appropriate tools in survival analysis, such as cumulative incidence estimate, Kaplan-Meier curves, and Cox regression with age, gender and ethnicity as covariates, which take consideration of both death without the event of interest as a competing risk and random censoring due to loss of follow-up. The Kaplan-Meier estimates and Cox regression will be used to evaluate the treatment effects on the overall survival. Graphical tools will be used to display the appropriate estimates (*i.e.* estimated proportions, the cumulative incidence curves, Kaplan-Meier curves) and their corresponding 95% confidence intervals. Exploratory subgroup analysis will be used to compare the possible different response rates among male, female and different age categories.

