# 3. Study Design

The study is designed as a single-site, non-randomized, single-arm pilot study of the oral TPOR agonist eltrombopag (EPAG) in Diamond-Blackfan anemia (Figure 3) to test the hypothesis: *eltrombopag improves the production of red blood cells in Diamond-Blackfan anemia patients.* The primary endpoint (see §8.2) is measured at 6 months (24 weeks ± 14 days). Subjects who cannot tolerate the medication or fail to respond by the primary endpoint will be taken off study drug. Subjects who *respond* at the primary endpoint (hemoglobin increase of 1.5 g/dL or more and/or transfusion independence for the previous 8 weeks, see §8.2.1) will be able to continue EPAG on the extension part of this protocol for an additional 3 years. During the 3-year extension phase, subjects will remain on the same dose of EPAG until they reach a *robust response* (defined as hemoglobin ≥10 g/dL in the absence of transfusions for more than 8 weeks, see §8.2.1). Drug dose will then be tapered slowly to the lowest dosage that maintains a stable hemoglobin (≥ 10 g/dL) and eventually discontinued if possible (per §5.3), until they meet off study criteria (see §8.6), or the study is closed. Drug will be restarted during extension if robust response is lost (*i.e.* hemoglobin falls below 9 g/dL).

Up to 30 subjects (18 for Stage 1 & 12 for Stage 2) will be screened to accrue 25 eligible subjects for this study.

[figure not shown]

Figure 3: Study enrollment and treatment schema

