# 6.2. Baseline labs

Laboratory evaluations performed as part of screening may be used if obtained within 7 days prior to consent. Screening results (§6.1) may be used as baseline studies if performed within 12 weeks or as indicted below.

- Complete blood count with differential (7 days or less prior to signing consent)
- Reticulocyte count (7 days or less prior to signing consent)
- Acute care panel (Na, K, Cl, CO2, Creatinine, Glucose, and Urea Nitrogen) (7 days or less prior to signing consent)
- Hepatic panel (Alkaline Phosphatase, ALT, AST, Total Bilirubin, and Direct Bilirubin) (7 days or less prior to signing consent)
- Pregnancy test (blood or urine hCG in women of childbearing potential) (7 days or less prior to signing consent)

The below baseline testing will be obtained once patient is consented onto study:

- MRI T2\* imaging to assess liver iron concentration
- Neurodevelopmental testing for patients less than 18 years of age (recommended, but at PI's discretion)
- 24-hour urine collection to determine the total iron (at PI's discretion)
- HLA typing

- HRQL survey administration
- Immunoglobulins
- Thyroid function panel (T3, T4, and TSH)
- Research blood as detailed in §7

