# 6.4. Landmark 3-month and 6-month evaluations

Subjects must be evaluated at the 3- and 6-month (± 14 days) time points. The 6-month time point shall be at the NIH Clinical Center. The 3-month assessment may be either at a home institution or at the NIH.

- Review of interval history and events
- Physical exam (may be omitted for 3-month evaluation if visit is not at the NIH)
- Complete blood counts with differential
- Acute care panel (Na, K, Cl, CO2, Creatinine, Glucose, and Urea Nitrogen)
- Mineral panel (Phosphorus, Magnesium, Albumin, and Calcium)
- Hepatic panel (Alkaline Phosphatase, ALT, AST, Total Bilirubin, and Direct Bilirubin)
- Other (Total Protein, CK, Uric Acid, and LDH) panel
- Reticulocyte count
- Iron panel (ferritin, transferrin, % saturation, total serum iron)
- Blood or urine pregnancy test (woman of childbearing potential only)
- Review of transfusion records (if available)

Additional assessments to be obtained at the NIH Clinical Center at the 6-month evaluation:

• Neurodevelopmental assessment for patients less than 18 years of age (if previously performed)

- Peripheral blood smear
- Hemoglobin F quantification by hemoglobin electrophoresis
- Erythrocyte adenosine deaminase
- Copper and zinc levels
- MRI T2\* imaging to assess liver iron concentration
- 24-hour urine collection to determine the total iron content at PI's discretion if indicated for iron metabolism and excretion studies
- Blood for pharmacokinetic evaluation of EPAG levels at PI's discretion. Samples drawn predose, and at 2-, 4-, 6- and 8-hour post-dose timepoints, with an optional final sample at 24 hours after dose
- Bone marrow aspiration and core biopsy, to be stained for standard morphologic analysis and quantitation of cellularity with hematoxylin and eosin, and special stains to assess reticulin and collagen, primitive stem and progenitor cells via CD34 immunohistochemistry, and other lineage-specific or special stains as indicated to classify any abnormalities
- Bone marrow chromosomal analysis via standard cytogenetic techniques
- HRQL survey administration
- Research blood as detailed in §7
- 6.5. Long term follow-up for responding patients enrolled in extended access phase

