- Bone marrow chromosomal analysis via standard cytogenetic techniques (every 6 months ± 30 days)
- HRQL survey administration (every 6 months ± 30 days)
- Iron panel (ferritin, transferrin, % saturation, total serum iron; every 6 months ± 30 days)
- MRI T2\* imaging to assess liver iron concentration (every 6 months ± 30 days during the first year of extended phase, and then if deemed necessary by the PI every 12 months ±30 days thereafter)
- 24-hour urine collection to determine the total iron content at PI's discretion if indicated for iron metabolism and excretion studies (every 6 months ± 30 days)
- Document Drug Accountability
- Review of interval history and events, and physical examination (every 6 months ± 30 days)
- Review of transfusion records (if available, every 6 months ± 30 days)
- Pediatric consult (every 6 months ± 30 days) at PI's discretion
- Research blood as detailed in §7 (every 6 months ± 30 days)
- 6.5.2. Subjects who have EPAG discontinued after tapering for a robust response during the extended access phase (see Table 3) will be followed in the following manner (up to 3 years after the 6-month visit):

- Complete blood counts with differential (monthly ± 10 days for 6 months off eltrombopag, then every 3 months ± 30 days until they reach off study criteria as per §8.6 or the study is closed)
- Ferritin (monthly ± 10 days for 6 months off eltrombopag, then every 3 months ± 30 days until they reach off study criteria as per §8.6 or the study is closed)
- Iron panel (ferritin, transferrin, % saturation, total serum iron; every 12 months ± 60 days)
- Hemoglobin F quantification by hemoglobin electrophoresis (every 12 months ± 60 days)
- MRI T2\* imaging to assess liver iron concentration (every 12 months ± 60 days if the PI deems necessary, if drug is discontinued during first year of extended phase, also obtain imaging at the 6-month visit as above in §6.5.1)
- Erythrocyte adenosine deaminase (every 12 months ± 60 days)
- Peripheral blood smear (every 12 months ± 60 days for three years)
- Bone marrow aspiration and core biopsy, to be stained for standard morphologic analysis and quantitation of cellularity with hematoxylin and eosin, and special stains to assess reticulin and collagen, primitive stem and progenitor cells via CD34 immunohistochemistry, and other lineage-specific or special stains as indicated to classify any abnormalities. (every 12 months ± 60 days for three years)

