#### 6.6. Off study assessment

We will offer patients a follow-up evaluation at the NIH 6 months following being taken off EPAG treatment either due to lack of response or for the other reasons listed in §8.6, but this visit will

not be required. If they do not return to the NIH, we will contact their primary hematologist for information on their current hematologic status 6 months following their final dose of EPAG, and then take them off study.

If patients do return to the NIH at 6 months (± 30 days) for the off-study assessment, the following may be performed, and then the patient will be taken off study:

- Review of interval history and events, and physical examination
- Neurodevelopmental assessment (if previously performed)
- CBC with differential
- Hemoglobin F quantification by hemoglobin electrophoresis
- Erythrocyte adenosine deaminase
- Acute care panel (Na, K, Cl, CO2, Creatinine, Glucose, and Urea Nitrogen)
- Mineral panel (Phosphorus, Magnesium, Albumin, and Calcium)
- Hepatic panel (Alkaline Phosphatase, ALT, AST, Total Bilirubin, and Direct Bilirubin)
- Other (Total Protein, CK, Uric Acid, and LDH)
- Reticulocyte count
- Peripheral blood smear
- Bone marrow biopsy with reticulin and collagen staining and aspiration with cytogenetics
- Research blood as detailed in §7
- Iron panel (ferritin, transferrin, % saturation, total serum iron)
- MRI T2\* imaging to assess liver iron concentration, if being followed per above
- 24-hour urine collection to determine the total iron content at PI's discretion if indicated for iron
- Review of transfusion records (if available)

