#### 8.2.2. Secondary endpoints

Secondary endpoints will include:

- Hematological responses at 3 months (as defined above)
- Time to response
- Best response, regardless of response status at primary endpoint
- Impact on platelet count and neutrophil count
- Relapse during the extension phase
- Clonal evolution, according to cytogenetic, mutational or flow cytometric markers
- Toxicities with extended duration of therapy
- The impact of treatment and treatment response on quality of life.
- Evaluation of neurodevelopmental changes at baseline and 6-month evaluations.
- Iron loading as measured by ferritin trends at each evaluation, and by iron staining of bone marrow biopsies at baseline and 6-month evaluations (and during extension at the PI's discretion)
- Evaluation of reactive oxygen species HSPCs (ROS flow cytometry assay at baseline and 6 months), and at interval evaluations during extended access at the PI's discretion

- Evaluation of global transcriptome in HSPCs (single cell RNA seq at baseline and 6 months)
- The impact of eltrombopag on reconstitution of the stem cell compartment (multicolor flow cytometry of bone marrow cells) and erythroid compartment (multicolor flow cytometry and CFU-E/BFU-E assays) at baseline and 6-month evaluations, and at interval evaluations during extended access at the PI's discretion

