## 8.5. Stopping rules

The study will be monitored to ensure that the occurrence of a specified set of treatment related serious adverse events (TRSAEs) that occur during the treatment period does not substantially exceed an anticipated rate. The following specified TRSAEs determined to be probably or definitely related to EPAG will be considered for early stopping of the study:

- 1. Death considered to be probably or definitely related to eltrombopag
- 2. Any Grade IV toxicity excluding readily reversible metabolic or laboratory abnormalities
- 3. Grade IV thrombosis/embolism

We anticipate the rate of these specified TRSAEs within the 24-week study period to be 20% or less. Following Geller *et al.* (90), our stopping rule is determined by a Bayesian approach. The stopping boundary for an experiment is reached if the Bayesian posterior probability that the true probability of developing one or more of the specified TRSAE's exceeds this benchmark rate of 20% is at least 90%. We take our prior distribution to be a beta distribution with parameters ( $\alpha$ ,  $\beta$ ) = (1, 4). The parameters are chosen so that the mean  $\alpha / (\alpha + \beta) = 0.2$  as the expected proportion of specified TRSAE's and the sum  $\alpha + \beta = 5$  as the "worth" we place on our prior clinical opinion. This indicates that the relative weight we place on our prior opinion is 5/25=20% of the weight we will place on the results of the new study. Hence when we make decisions about stopping the study, the data from the study will dominate over the prior opinion. All participants will be included in monitoring and evaluation for safety. Table 5 summarizes the threshold numbers for stopping the study.

Number of subjects in the experiment	Stop if the number of subjects who have developed any of the specified TRSAE's reaches:
≤ 5	3
≤ 9	4
≤ 12	5
≤ 16	6
≤ 20	7
≤ 24	8

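### No quality-of-life survey is clearly scheduled for subjects who stop eltrombopag before month 6, and 8.4 names no time point or analysis set, so the tested change may favor treatment

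*Combined protocol and SAP*

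**What the plan says.** Sections 1 and 8.1 list health-related quality of life among the secondary objectives, and section 8.2.2 gives the endpoint as "The impact of treatment and treatment response on quality of life". The whole analysis plan for it is in section 8.4: "The change of quality of life measure from baseline will be examined by the t-test or the nonparametric rank-based test". That section says nothing about when the change is measured, who is included, or what happens when a survey is missing.

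The survey schedule is spread over several places:

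- **Baseline and month 6.** Sections 6.2 and 6.4 each list "HRQL survey administration", and Table 14 marks the same two visits. The month-6 entry is not limited to responders. A note to Table 14 limits the survey to adults who read English or Spanish.
- **Extension.** Section 6.5 admits only subjects who meet the response criteria at month 6. On drug, section 6.5.1 has "HRQL survey administration (every 6 months ± 30 days"). Robust responders who have tapered off drug are surveyed every 12 months (6.5.2).
- **Stopping drug.** Section 3 states: "Subjects who cannot tolerate the medication or fail to respond by the primary endpoint will be taken off study drug". Sections 6.6 and 8.6 then offer a visit six months after the last dose, which is not required. At that visit "the following may be performed, and then the patient will be taken off study". The list includes neurodevelopmental assessment, bone marrow biopsy, MRI and research blood, but not HRQL. The HRQL rows of Tables 14 and 15 are blank in the off-study columns.
- **Landmark rule.** Section 6.4 states: "Subjects must be evaluated at the 3- and 6-month (± 14 days) time points". It does not say whether this applies to a subject already off drug.

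**The concern.** A change from baseline needs a later survey. The plan clearly provides one for subjects still on drug at month 6, whether or not they respond, and for responders afterwards. It does not clearly provide one for subjects who stop before month 6.

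Those subjects are not a random subset. Section 8.6 lists intolerance, hypersensitivity, persistent hepatotoxicity, treatment-related Grade IV toxicity and thrombosis among the reasons for stopping. Section 9.2.2 adds drug discontinuation for most laboratory abnormalities above grade 2. Many of these events could plausibly worsen quality of life.

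There is no control arm, so this change score is the main evidence on the objective. If subjects who fared badly are missing from it, the score describes those who tolerated treatment rather than those who were treated. Surveys that were never given cannot be recovered at analysis.

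**Working it through.** **1. Plan figures.** The plan gives no sample size, standard deviation, power or discontinuation rate for HRQL, so there is no HRQL figure to reproduce. The total of 25 in section 8.3 belongs to the response endpoint. It does reproduce: the exact two-stage calculation gives type I error 0.033 and power 0.802. It bears on HRQL only as an upper limit on the number surveyed.

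**2. Who has a scheduled survey after baseline** (adults who read English or Spanish):

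| Subject | Month 6 | After month 6 |
|---|---|---|
| Responder, continues on drug | Yes (6.4) | Every 6 months (6.5.1) |
| Robust responder, tapered off drug | Yes (6.4) | Every 12 months (6.5.2) |
| Non-responder who reaches month 6 | Yes (6.4) | None |
| Stops drug before month 6 | Not stated | None (6.6; Tables 14 and 15) |

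**3. Timing for the last row.** If drug stops at month s, with s below 6, the optional visit falls at month s + 6. For s = 2 that is month 8. So calendar month 6 always comes before the off-study visit. Under 6.6 and 8.6 many such subjects are still on study at month 6, and a survey would be feasible. The exceptions are subjects who leave at once, as section 5.5.1 provides for thrombosis, and those who start alternative therapy, whose participation ends under section 8.6.

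**4. Size at month 6 (illustration).** Let m be the fraction that stops early without a later survey, d the mean change in completers and c the mean change in early stoppers.

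- All-treated mean = (1 − m)d + mc.
- Relative overstatement = d / [(1 − m)d + mc] − 1.
- With c = 0 and m = 0.10: 1/0.90 − 1 = 11%.
- With c = 0 and m = 0.20: 1/0.80 − 1 = 25%.
- With c = −0.5d and m = 0.10: 1/(0.90 − 0.05) − 1 = 18%.
- With c = −0.5d and m = 0.20: 1/(0.80 − 0.10) − 1 = 43%.

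In standard deviation (SD) units the bias is m × g, where g is the completer mean minus the early-stopper mean:

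| m | g = −0.5 | g = 0 | g = 0.5 | g = 1.0 |
|---|---|---|---|---|
| 0.10 | −0.05 | 0 | 0.05 | 0.10 |
| 0.20 | −0.10 | 0 | 0.10 | 0.20 |
| 0.30 | −0.15 | 0 | 0.15 | 0.30 |

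Suppose the true all-treated change is zero and all 25 subjects are eligible for the survey. Over the cases with g of 0.5 or 1.0, a two-sided 0.05 one-sample t-test in completers then rejects between 5.6% (m = 0.10, g = 0.5) and 22.5% (m = 0.30, g = 1.0) of the time.

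**5. Numbers of people.** With 25 subjects, 10% to 20% is 2.5 to 5 people. It is fewer among those surveyed, because children and adults who read neither language are not.

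**6. After month 6.** At the hypothesized 30% response rate, 0.30 × 25 = 7.5, so about 8 subjects supply all later HRQL data, and all are responders.

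**The case against.** The strongest reply is that section 6.4 already requires a month-6 evaluation of subjects without limiting it to those on drug, and that early stoppers are generally still on study at that date. On that reading the survey is scheduled. It is a possible reading. But 6.6 and 8.6 set out a separate path for these subjects, timed from the last dose, optional and without HRQL. What stands is that the text is ambiguous, not that it excludes them outright.

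A second reply is that nothing establishes how many will stop early or how they will fare. This stands. The benchmark in section 8.5, "We anticipate the rate of these specified TRSAEs within the 24-week study period to be 20% or less", is an upper safety limit on specified events, not a discontinuation rate. The 14% withdrawal for adverse events in section 2.4.6 comes from an extension study in immune thrombocytopenia with median exposure of 2.4 years, against 24 weeks here. Section 2.4.3 reports 43 patients with aplastic anemia escalated to 150 mg without dose-limiting toxicity. Missingness could be low, and zero or downward bias is possible.

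A reader might also infer that the change is tested only in subjects who stay on drug. The documents do not support that: non-responders who reach month 6 and robust responders tapered off drug are both surveyed. Another tempting inference is a responder-only test at later visits, with a mean 1/0.30 = 3.3 times the all-treated mean. Section 8.4 states no such test, the factor assumes no change in non-responders, and the endpoint includes the impact of response, for which responder data are relevant.

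Finally, this is one of many secondary endpoints in an uncontrolled pilot, with no decision rule attached. Complete surveys would still not make a before-after change causal. That limits the weight of the point.

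**Conclusion.** The point holds in limited form. Section 8.4 does not fix the time point, analysis set or handling of missing surveys for HRQL. The early-discontinuation path has no HRQL survey, and the only text that might supply one is ambiguous. The month-6 change may therefore be biased, probably in favor of treatment, since many listed reasons for stopping are harms.

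That direction is a judgment. It would be wrong to say that the plan is shown to overstate the effect. The 11% to 25% range assumes that 10% to 20% stop early and do not change, and neither assumption comes from the documents. Data after month 6 describe responders only and should be labelled so. The primary endpoint and the stopping rule are unaffected. The change is worth making because it is cheap and the lost surveys cannot be recovered.

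**What to change.** 1. **Collection (6.4, 6.6, 8.6, Table 14).** Give the existing survey at drug discontinuation and at calendar month 6 regardless of drug status, remotely if needed, to every subject with a baseline survey who is still on study. For subjects who go off study at once or start alternative therapy, use the survey at discontinuation. This respects the rule in 8.6 that ends participation and avoids mixing in the effect of another therapy. No treatment or stopping rule changes.
2. **Analysis (8.4).** Name month 6 as the time point of the HRQL test, in all treated subjects with a baseline survey. Use the discontinuation survey when there is no month-6 survey. Report the number surveyed against the number eligible. Add a simple sensitivity analysis that assigns no change, then a worsening of a size fixed in advance, to subjects with no later survey. A repeated-measures model is optional at this sample size.
3. **Later data.** Report HRQL after month 6 descriptively, as results in responders, including those tapered off drug.

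The cost is one or two extra questionnaires for the few who stop early, some schedule edits and a few sentences in 8.4. The reported change may be smaller. No new instrument or staff is needed.

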# 8. Biostatistical Considerations

## 8.1. Objectives

The *primary objective* is to evaluate safety and efficacy of 6 months of therapy with eltrombopag in subjects with Diamond-Blackfan anemia.

The *secondary objectives* include assessments of the impact of eltrombopag upon rates of relapse and survival, clonal evolution, toxicities of extended therapy, the impact of treatment upon healthrelated quality of life and neurodevelopment in pediatric patients, and the impact of eltrombopag upon stem cell and erythroid cell dynamics and niche interactions including iron homeostasis.

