# 8.6. Off study criteria

*Per subject choice:* Subjects may withdraw from study at their request. The risks of withdrawing will be discussed, as will alternative treatment options. Those subjects who choose to withdraw while taking eltrombopag will be strongly encouraged to continue to have labs monitored until he/she initiates alternative therapy.

**Per principal investigator decision:** Should any of the following events occur during the study period, or in the extension treatment arm in responders, EPAG will be discontinued. The subject will be followed until resolution of the event. For study purposes labs relevant to the adverse event will be monitored for 30 days after discontinuation of EPAG. We will offer patients a follow-up evaluation at the NIH 6 months following being taken off EPAG treatment either due to lack of response or because they met other criteria for coming off study, but this visit will not be required. If they do not return to the NIH, we will contact their primary hematologist for information on their current hematologic status 6 months following their final dose of eltrombopag, and then take

them off study. If a patient initiates an alternative disease directed therapy at any time, the subject's participation on this study will be considered complete and the subject will go off study.

- Intolerance of EPAG not resolved by dose reduction
- Life threatening acute hypersensitivity reaction
- Thrombosis/embolism (DVT, PE, stroke or TIA, myocardial infarction) other than central line thrombosis
- Persistent hepatotoxicity as defined in §10.3.1
- New or worsening morphological abnormalities or cytopenia(s) indicative for transformation to MDS or AML
- No treatment response by week 24 (+/- 7 days)
- Any Grade IV toxicity considered related to the study medication excluding readily reversible metabolic or laboratory abnormalities or hematologic toxicities (see §9.2.1, 10.3.1)
- Significant progression of disease such as development of a solid tumor while on EPAG, or a concomitant condition that would make the subject ineligible for further protocol participation
- Pregnancy or unwillingness to use acceptable forms of contraception
- Initiation of non-protocol therapy for Diamond-Blackfan anemia
- Subject non-compliance
- Lost to follow-up

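### A single-arm trial cannot estimate the treatment effect on overall survival that section 8.4 plans to evaluate, and its survival curve after about month 12 rests on responders only

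*Combined protocol and SAP*

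**What the plan says.** Section 3 describes a "single-site, non-randomized, single-arm pilot study". Survival is a secondary objective: section 8.1 lists "assessments of the impact of eltrombopag upon rates of relapse and survival". The endpoint list in section 8.2.2 does not include overall survival. No time origin or censoring rule for it is given, and no historical or external survival control is named.

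The analysis is in section 8.4: "The Kaplan-Meier estimates and Cox regression will be used to evaluate the treatment effects on the overall survival". The preceding text, on time to response and progression-free survival, offers as example tools cumulative incidence, Kaplan-Meier and "Cox regression with age, gender and ethnicity as covariates". The only censoring that section 8.4 mentions is there too: "random censoring due to loss of follow-up".

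Follow-up depends on outcome. Under section 8.6, a subject without a response at about week 24 stops drug. Section 6.6 offers an optional visit six months later; failing that, "we will contact their primary hematologist for information on their current hematologic status 6 months following their final dose of EPAG", after which the subject is off study. Responders may continue for three years (sections 6.5 and 8.6). Section 8.6 also ends participation whenever another treatment for the disease is started, and section 5.5.1 takes subjects with a thrombotic event off study.

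**The concern.** A treatment effect needs a contrast between treated and untreated survival. This trial collects only treated subjects and the plan imports no comparison, so the sentence promises a quantity that the data cannot supply.

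The curve itself has a second problem. Kaplan-Meier treats a subject who leaves as having the same future risk as those who stay. Here, leaving is tied to failure to respond, a change of therapy or a serious event. After non-responders go off study, what looks like survival of the treated population is survival of those who did well enough to remain. At stake is how a stated secondary objective is reported, and how far a reader can trust the tail of the curve.

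**Working it through.** **1. The plan's own figure.** Section 8.3 sizes the trial for response only: a two-stage design with 1/15 and 5/25 as the futility limits. With b(15, x, p) the binomial probability of x responders in stage 1 and Y ~ Bin(10, p), the rejection probability is the sum over x = 2 to 15 of b(15, x, p) × P(Y ≥ 6 − x). It is 0.0328 at p = 0.10 and 0.8017 at p = 0.30, so n = 25 meets the stated 0.05 and 0.80. The documents give no number of deaths, power or precision for survival.

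**2. The treatment term.** In the Cox partial likelihood, each death contributes exp(βz + γx) for the subject who died, divided by the sum of the same quantity over all at risk. With z = 1 for everyone, exp(β) cancels from top and bottom. The likelihood does not depend on β, and its score and information are zero. A numerical check on 25 made-up subjects with 3 deaths, fitting treatment, age, gender and a two-level ethnicity, gave score 0 and information 0 for treatment, and an information matrix of rank 3 instead of 4. There is no hazard ratio for treatment to report.

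**3. Follow-up.** Non-responders: about 24 weeks on drug plus 6 months, or about 1.0 year. Responders: 0.5 + 3 = 3.5 years. With n = 25 and the design response rate of 30% (section 8.3), and no earlier exits:

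- Person-years = 25 × (0.30 × 3.5 + 0.70 × 1.0) = 25 × 1.75 = 43.75.
- Expected responders = 25 × 0.30 = 7.5; subjects leaving by about month 12 = 25 × 0.70 = 17.5.
- Person-years after month 12 = 7.5 × 2.5 = 18.75, all from responders.

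**4. Expected deaths.** The death rate is an assumption. Expected deaths = person-years × rate; P(no deaths) = exp(−expected deaths). For 43.75 person-years:

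| Assumed rate per year | Expected deaths | P(no deaths) |
|---|---|---|
| 0.5% | 0.22 | 0.80 |
| 1% | 0.44 | 0.65 |
| 2% | 0.88 | 0.42 |
| 5% | 2.19 | 0.11 |

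Sensitivity to response rate and to stopping after stage 1:

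| n | Response | Person-years | Expected deaths at 0.5% to 5% |
|---|---|---|---|
| 15 | 10% | 18.75 | 0.09 to 0.94 |
| 25 | 10% | 31.25 | 0.16 to 1.56 |
| 25 | 50% | 56.25 | 0.28 to 2.81 |

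None of these supports a Cox model with three covariates.

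**5. Exits before month 12.** Starting other disease-directed treatment ends participation at once (section 8.6). Thrombosis leads off study (section 5.5.1). Other reasons listed in section 8.6, such as transformation to MDS or AML, stop the drug, with one further contact six months after the last dose. A subject who stops at month 2, for example, would be last seen at about month 8. These exits plausibly relate to prognosis, so they are not covered by an assumption of random loss.

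**6. What a descriptive analysis can give.** If all 25 had known status and none died, the exact upper limit for the death proportion would be 1 − 0.05^(1/25) = 11.3% (one-sided 95%), or 1 − 0.025^(1/25) = 13.7% (two-sided 95%). This is the best case; early exits would weaken it.

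**The case against.** The strongest defence is that the sentence is loose wording. Survival is not in the endpoint list, no decision rule uses it, and a Kaplan-Meier curve of treated subjects is a normal thing to show. A Cox model with baseline covariates can be fitted in principle. All of that stands, and it limits the weight of the point. It does not rescue the sentence: it commits to Cox regression for a treatment effect, and prognostic associations are not one.

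Some stronger readings are tempting, but the documents do not support them:

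- *The trial would publish a false survival benefit.* A constant treatment term yields no estimate, so an empty analysis is the likelier result. The real risk is over-reading the responder-only tail.
- *The analysis carries immortal-time bias.* That would arise from comparing survival of responders and non-responders from first dose. Section 8.4 proposes no such comparison.
- *Long-term clonal-evolution curves would be biased in the same way.* Clonal evolution is a secondary endpoint, but section 8.4 specifies no time-to-event curve for it.
- *Cox for time to response has at most 2.5 events per coefficient (7.5/3).* That is an expectation at 30%, the lowest rate in the alternative hypothesis. Section 8.2.1 counts the first time that criteria are met, so transient responders add events. Cox is also only one of the example tools there.
- *Twelve months is complete common follow-up.* The exits in step 5 show that it is not.

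**Conclusion.** The point holds for overall survival. The planned treatment effect is not estimable; this follows from the design and needs no assumption. That a covariate-only Cox model would probably be empty or unstable rests on the assumed death rate of 0.5% to 5% per year; a much higher rate would be needed to change it. That the curve after about month 12 describes responders only follows from the off-study rules. At 30% response, 7 or 8 of 25 subjects remain if all responders continue, contributing 18.75 of at most 43.75 person-years. The direction and size of any bias from earlier exits cannot be derived from the documents; the censoring can only be called possibly informative. This is a secondary analysis that should be corrected before reporting. It does not affect the primary response test, n = 25 or the safety stopping rule.

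**What to change.** In section 8.4, delete the reference to treatment effects and the Cox model for overall survival. Replace them with a descriptive plan:

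- Report the number of deaths and a Kaplan-Meier curve from first dose for all treated subjects, up to about 12 months.
- State beside it how many subjects left earlier and for which reasons, and that this censoring may be informative.
- Label every later survival result *among responders continuing in the extension*.

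The change is to analysis wording only. It adds no subjects or visits and leaves treatment rules as they are. Its cost is a narrower survival statement: a description of treated subjects to about a year, then of a selected group, with no claim about what eltrombopag does to survival.
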